### 5.3. Populations for Analyses

#### **Table 4 Analysis Sets**

Analysis Set	Description
Screened Set	All patients consented
Randomised Set	All patients in the Screened Set who are assigned to a randomisation group
Safety Analysis Set	All patients in the Randomised Set
Primary Analysis Set	All patients in the Randomised Set excluding participants with major violations of the clinical investigation plan
Extension Set	All patients in the Randomised Set who participate in the extension period

#### 5.4. Data Analyses

#### **5.4.1.** General Considerations

The analysis plan will be fully described in a written and approved statistical analysis plan (SAP). Descriptive analyses will be performed on the Screened Set and the Randomised Set to gain an understanding of the qualitative and quantitative nature of the data collected and the characteristics of the sample studied. If more than 15% of randomised participants will be excluded from the Primary Analysis Set, the baseline descriptive analysis will be repeated on the primary endpoint analysis population.

Primary and secondary endpoint analyses will be performed before the end of the study, after the last enrolled participant has completed the Day  $56 \pm 7$  days assessments.

Applicable analyses will be repeated as descriptive at the end of the study to include the extension period assessment and will be based on the Extension Set.

All computations and generation of tables, listings and data for figures will be performed using Statistical Analysis System (SAS)® version 9.4 or higher (SAS Institute, Cary, NC, USA).

Continuous variables will be reported as mean (and standard deviation [SD]) along with median and range where appropriate. Categorical variables will be summarised as number and proportion of the total study population, and by age subgroups (4–<6 years and  $\geq$ 6–8 years) where appropriate.

In general, descriptive statistics of quantitative parameters (result and change from baseline) by scheduled visits will be provided on observed cases, that is, patients having non-missing assessments at a specific visit.

Individual patient data will be presented in listings considering the Screened Set.

All AE verbatim terms will be recorded and coded by system organ class (SOC) and preferred term (PT) using the Medical Dictionary for Regulatory Activities (MedDRA).

#### **5.4.2.** Planned Analyses

The total number of patients included in each analysis set along with the number of patients for each of following categories will be provided as disposition analysis:

- Patients consented, overall and by age group  $(4-<6 \text{ years and } \ge 6-8 \text{ years})$
- Patients randomised, overall and by age group  $(4-<6 \text{ years and } \ge 6-8 \text{ years})$
- Patients who completed the 4-week intervention period, overall and by age group  $(4-<6 \text{ years and } \ge 6-8 \text{ years})$
- Patients who entered the extension period, overall and by age group (4–<6 years and  $\ge$ 6–8 years)
- Patients who completed the extension period, overall and by age group (4-<6 years) and  $\ge 6-8 \text{ years})$
- Time and reasons for discontinuation of the study, overall and by age group  $(4-<6 \text{ years and } \ge 6-8 \text{ years}).$

For all categories except the Screened Set, the percentages will be calculated using the number of randomised patients as the denominator for each treatment group.

Baseline will be defined as the data collected at or prior to randomisation; demographic and baseline characteristics, disease history, physical examination, medical history and concomitant medication will be summarised with appropriate descriptive statistics by group and separately for age subgroups.

These summaries will be provided for the Screened and Randomised Sets.

Body height, body weight and BMI will be summarised. The calculated BMI will be classified as follows based on comparison with:

- Underweight (<5th percentile for sex and age),
- Normal (from 5th to less than 85th percentile for sex and age),
- Overweight (from 85th to less than the 95th percentile for sex and age),
- Obese ( $\geq 95^{th}$  percentile for sex and age).

Physical examination will be summarised as percentage of patients with normal/abnormal result overall and as per the physical examination features listed in Section 4.5.3.2.

Pathologies associated with past medical or surgical history will be summarised by primary SOC and PT as per MedDRA. Concomitant therapies will be summarised by Anatomical Therapeutic Chemical (ATC) Classification System.

Direct- to-patient data will be analysed descriptively at each assessment along with applicable change from baseline on the Randomised Analysis Set and Primary Analysis Set.

The primary outcome (i.e., average number of wet nights in Week 4 of the core study period) will be analysed for the Primary Analysis Set comparing the 95% CI for the difference between the means of the 2 groups with the predefined margin ( $\delta = 2/7$ ). If the CI lies strictly within [- $\delta$ , + $\delta$ ], the study hypothesis will be demonstrated.

QoL and sleep quality endpoints will be assessed analysing the following questionnaires:

- Paediatric Incontinence Questionnaire
- World Health Organization Quality of Life
- Paediatric Daytime Sleepiness Scale
- Checklist Individual Strength

The PinQ measures the emotional impact that urinary incontinence has on a child. It consists of 20 urinary incontinence QoL related questions which are graded on a scale of 0–4 (0=No, 1=Hardly ever, 2=Sometimes, 3=Often, 4=All the time) with a total possible score of 80.

The total score indicates the impact urinary incontinence has on the child's QoL with the higher score indicating a more significant effect.

The WHOQoL-BREF assesses the individual's perceptions in the context of their culture and value systems, and their personal goals, standards, and concerns. It comprises 26 items, which measure the following broad domains: physical health, psychological health, social relationships, and environment. Domain scores are scaled in a positive direction (i.e., higher scores denote higher QoL). The mean score of items within each domain is used to calculate the domain score. Mean scores are then multiplied by 4 in order to make domain scores comparable with the scores used in the WHOQoL-100 (WHO 1996).

The PDSS questionnaire has been developed to measure daytime sleepiness of middle-school children and examine the relationship between daytime sleepiness and school-related outcomes. It consists of 8 items (0–4-point scale) with higher scores associated with reduced total sleep time, poorer school achievement, poorer anger control, and frequent illness. The total score will be calculated as sum of each item response.

The CIS is a 20-item fatigue questionnaire for which the person indicates on a 7-point scale to what extent a particular statement applies to him or her and it measures 4 dimensions of fatigue: fatigue severity (items 1, 4, 6, 9, 12, 14, 16, 20), concentration problems (3, 8, 11, 13, 19), reduced motivation (2, 5, 15, 18) and activity (7, 10, 17). The CIS total score can be calculated by adding the 4 dimensions.

Analyses of these 4 questionnaires will be provided by group on the Randomised Set. Frequency distribution and descriptive statistics, when applicable, will be provided by visit for each item of questionnaires, while summary statistics for total scores, domain scores and changes from baseline will be provided as applicable for the PinQ, WHOQoL-BREF, PDSS and CIS.

The effect size will be also presented as descriptive statistics of ratio between the change from baseline and baseline SD.

The percentage of patients with change from baseline  $\geq 0.5$  time the SD will be also provided. For applicable questionnaires, a covariance analysis model (ANCOVA) with baseline PROs value as covariate will be performed. Group comparisons will be performed for the difference in least squares means (LSMean) at Day  $56 \pm 7$  days. LSMean (standard error [SE]) by group and visit (if applicable), the LSMean difference between groups, along with 95% confidence limits of the group differences and the p-value for the group comparison will be displayed. For the change from baseline, p-value for the within-group difference will also be displayed.

The same analysis will be repeated using a repeated measure model to assess the extension period effects.

The Absorbent Pants Clinical Trial Questionnaire administered at study entry, and the DryNites® Clinical Trial Questionnaire administered at the end of the run-in period, will be analysed descriptively for the Screened Set.

#### **5.4.3.** Exploratory Analyses

An exploratory analysis will be presented describing data collected over the extension period. Additional exploratory analyses may be performed and will be outlined in the SAP prior to analysis.

## 5.4.4. Safety Analyses

All safety analyses will be performed on the Safety Analysis Set.

AEs are reported since ICF signature, throughout the patients' discontinuation of the study.

Treatment-emergent adverse events (TEAEs) are defined as AEs that first occurred or worsened in severity after randomisation and prior to the end of the extension period.

AEs that occurred from ICF signature till randomisation will be described separately.

AEs will be coded using MedDRA. For each group, numbers and proportion of TEAEs, device-related TEAE and serious TEAEs will be tabulated by SOC and PT.

Medical Device Incidents not associated with a TEAE will be described separately.

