# 4 METHODOLOGY

# 4.1. Study Design

This is an 8-week randomised, open-label, 2-arm, parallel-group Phase IV trial with a 2:1 allocation ratio for discontinuation of continuation of use of DryNites® absorbent pants in children with NE, with an optional 4-week extension period. This will be an equivalence trial for the primary endpoint.

Eligible patients are children with monosymptomatic NE, not previously treated for NE, and managed with absorbent pants/nappies (any brand) for a minimum of 6 months. Participants must be dry at day for at least 6 months. Participants will be divided in 2 age groups of similar

size. The younger age group will be comprised of participants aged 4-<6 years old and the older age group will be comprised of participants aged  $\ge 6-8$  years old. Capping of the faster recruiting subgroup will be implemented if needed.

Participation in the study will be proposed for all children meeting the above conditions; parents/carers should be given sufficient time to review the study information and provide informed consent to their child's and their participation. Children's assent will be requested for the older age group.

The study consists of 3 consecutive periods of 4 weeks each, including the run-in, the intervention (core trial) period, and the extension period.

Participant meeting the eligibility criteria will enter the run-in period. During the 4-week run-in period, all participants will be assigned to using DryNites® every night.

Participant meets the inclusion criterion of NE 7 nights per week during the last week of the run-in period will be randomised to participate in the intervention (core trial) period. During the 4-week intervention period, participants will be assigned to either stopping the use of absorbent pants or continuing DryNites® in a 2:1 ratio. All participants will receive absorbent bed mats to use every night, however, the use of bed mats is optional.

Following completion of the 4-week intervention period, participants will be invited to participate in the optional 4-week extension. During the optional 4-week extension period, participants will remain on their randomly assigned treatment for an additional 4 weeks.

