### 4.5.3. Other Assessments

#### 4.5.3.1. Willingness to Continue in the Extension Period

If the child or parents/carers do not wish to participate in the extension trial, their reasons for non-participation will be recorded in the eCRF on Day  $56 \pm 7$ .

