#### **5.4.6.** Limitations of Research Methods

The intention of this Phase IV study is to collect data on the impact of absorbent pants on the spontaneous resolution of NE, as well as children and parents/carers QoL and sleep quality. The primary endpoint relies on the completion of a diary by the participant's family. Failure to adhere to the clinical investigation plan and complete the diary information may result in a significant amount of missing data. Information bias will be minimised by using standard eCRF, questionnaires and physicians' training on the study clinical investigation plan. The patients' interpretation and understanding of the questionnaires and different educational backgrounds may also influence the results.

The sites selected will be a convenience sample and may not be representative of the geographic distribution or the clinic/hospital type or size in each of the participating countries. The enrolment will be competitive. At the patient level, consecutive enrolment will be employed to minimise selection bias. Potential selection bias arising from the lack of complete enrolment of potentially eligible patients will be reduced by maintaining screening logs at sites.

Several features of this study have been selected based on the experience of the members of the Scientific Committee. In order to reduce the heterogeneity of the patient population, the study will randomise patients who present with NE every night for 7 months (6 months prior to

baseline, and the 4-week run-in period). These characteristics are shared by most of the patients referred to specialist care. However, selection of patients from hospital/clinic-based specialist care may not be representative of the pool of patients with NE assessed in the community setting by paediatricians and general practitioners.

The equivalence margin of 2 dry nights per week has been determined based on the feedback of patients and families; they would not consider an effect of only 1 night a week clinically significant.

The intervention period is limited to 4 weeks; a longer period may not be acceptable for families. The likeliness of observing a spontaneous resolution of NE in this 4-week period is limited, which carries the risk of concluding to the equivalence of the 2 treatment strategies by lack of any change in either group. The duration of the study period should be kept in mind in the interpretation of the study results.

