#### 7 SAFETY REPORTING

All AEs, regardless of relationship to the study treatment or intervention, will be monitored and reported throughout the entire course of the study. The AE reporting period begins when the patient is consented to participation in the study (date of first signature of informed consent) and continues through the study discontinuation date. AEs will be recorded on the appropriate eCRF forms.

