16. SAFETY OUTCOMES

All outputs for safety outcomes will be based on the Safety Analysis Set.

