16.1 Adverse Events

Adverse Events (AEs) will be coded using the version of MedDRA available at the time of the analysis.

Treatment emergent adverse events (TEAEs) are defined as AEs that first occurred or worsened in severity after the start of screening period and prior to the end of the extension period.

See Appendix 1 for handling of partial dates for AEs. In the case where it is not possible to define an AE as treatment emergent or not, the AE will be classified by the worst-case scenario; i.e. treatment emergent.

The AEs that occurred from ICF signature till randomisation will be described separately and presented in a listing.

For each group, numbers and proportion of TEAEs, device-related TEAE and serious TEAEs will be tabulated by SOC and PT along with number of events.

Medical Device Incidents (MDI) not associated with a TEAE will be described separately in a listing.

Document:	Y:\Kimberly-Clark\DryNites\Documentation\SAP\DryNites_SAP_v1.0_20200203		
Author:	[name]	Version Number:	1.0
		Version Date:	03Feb2020
Template No.: I	RWI_TP_BIOS0013 Revision 1		Reference: RWI_WI_BIOS0015

Effective Date: 15Jun2018

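### Treatment-emergent AEs are counted to the end of an optional extension with no cut at Visit 3, so the per-arm proportions cover unequal follow-up if extension uptake differs between arms

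*Protocol*

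**What the plan says.** **Window.** Protocol 5.4.4 defines TEAEs as "AEs that first occurred or worsened in severity after randomisation and prior to the end of the extension period". SAP 16.1 moves the start but keeps the end: AEs that "first occurred or worsened in severity after the start of screening period and prior to the end of the extension period". SAP 4.3 lists the earlier start as a change from the protocol. Protocol version 3.0, which is later than the SAP, still starts at randomisation.

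**Extension.** Under Protocol 4.1, after the 4-week intervention period, "participants will be invited to participate in the optional 4-week extension". The choice lies with the family and is made at Day 56: "If the child or parents/carers do not wish to participate in the extension trial, their reasons for non-participation will be recorded in the eCRF" (Protocol 4.5.3.1). The trial is open-label, so the choice follows 4 weeks' experience of a known assignment.

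**End of collection.** Under Protocol 7, AE reporting "continues through the study discontinuation date". For a child who declines the extension, that is about Visit 3.

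**Tables.** SAP 16.1: "For each group, numbers and proportion of TEAEs, device-related TEAE and serious TEAEs will be tabulated". SAP 16.1.1 counts a child once per system organ class or preferred term and gives the number of events alongside. SAP 16: "All outputs for safety outcomes will be based on the Safety Analysis Set". Under both definitions that set includes children who decline the extension and children who enter it. The SAP's exposure section (14) is marked not applicable. The only period shown separately is the one before randomisation.

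**The concern.** A proportion of children with at least one event rises with the time they are watched. Here that time depends on a choice made after randomisation by families who know their arm. If one arm keeps more children in the extension, it will show a higher proportion with an AE even when the underlying risk is the same. If it keeps fewer, a real excess could be partly hidden.

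The tables most affected are all-cause and serious TEAEs. Under Protocol 7.1.5, relationship to the device is not assessed in the discontinuation arm after randomisation, so device-related events cannot be compared like for like anyway. Protocol section 2 says the side-effects of the product have not been studied. It also describes a Class I product marketed since 1995, with only minor effects expected. The stake is therefore a misread descriptive table; nothing suggests a missed serious hazard.

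**Working it through.** The documents give no AE risk, no expected uptake and no precision for safety, so there is no planned figure to reproduce.

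**Inputs from the documents.** Run-in, intervention and extension last 4 weeks each (Protocol 4.1). Collection stops at discontinuation (Protocol 7). Each child counts once per category (SAP 16.1.1). The target is 120 randomised at 2:1, so 120/3 = 40 continue DryNites and 80 discontinue.

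**Assumptions.** The AE hazard is constant and the same in both arms. The risk per 4 weeks is r, and S = 1 − r. The proportion entering the extension is u. There is no other dropout, and visits fall on their nominal days. The figures are for randomised children.

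**Formulas.**
- Protocol window (from randomisation): mean follow-up 4(1 + u) weeks; proportion with an event 1 − [(1 − u)S + uS²].
- SAP window (from screening, adding the run-in): mean follow-up 8 + 4u weeks; proportion 1 − [(1 − u)S² + uS³].

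**Worked case, r = 10%, S = 0.90.**
- Protocol, u = 0.8: 1 − (0.2 × 0.90 + 0.8 × 0.81) = 0.172.
- Protocol, u = 0.4: 1 − (0.6 × 0.90 + 0.4 × 0.81) = 0.136.
- SAP, u = 0.8: 1 − (0.2 × 0.81 + 0.8 × 0.729) = 0.255.
- SAP, u = 0.4: 1 − (0.6 × 0.81 + 0.4 × 0.729) = 0.222.

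| Window | Uptake, DryNites vs no pants | Mean weeks | Proportion with an event | Ratio |
|---|---|---|---|---|
| Protocol | 80% vs 40% | 7.2 vs 5.6 | 17.2% vs 13.6% | 1.26 |
| Protocol | 80% vs 60% | 7.2 vs 6.4 | 17.2% vs 15.4% | 1.12 |
| Protocol | 80% vs 80% | 7.2 vs 7.2 | 17.2% vs 17.2% | 1.00 |
| SAP | 80% vs 40% | 11.2 vs 9.6 | 25.5% vs 22.2% | 1.15 |
| Cut at Visit 3 | any | 4 vs 4 | 10% vs 10% | 1.00 |

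Swapping the uptakes reverses the direction. The excess follow-up at 80% vs 40% is 7.2/5.6 = 1.29 on the Protocol window and 11.2/9.6 = 1.17 on the SAP window. Varying the risk on the Protocol window at the same uptakes gives 8.8% vs 6.9% at r = 5% and 32.8% vs 26.4% at r = 20%. The ratio depends far more on the uptake gap than on r.

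**Against chance.** With 40 and 80 children, the standard error of 17.2% − 13.6% is √(0.172 × 0.828/40 + 0.136 × 0.864/80) = 0.071. The 3.6-point artefact is about half of that.

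**Does any other section supply the cut?**
- Protocol 5.4.1 puts the end-of-study repeats on the Extension Set, whereas Protocol 5.4.4 and SAP 16 keep all safety outputs on the Safety Analysis Set.
- SAP 15.3 speaks of refreshing the AE analysis with extension data, which implies an earlier run but states no cut for it.
- SAP 5.2 times the earlier analysis at the last randomised child's completion of the intervention period and names only primary and secondary endpoints. After 30 months of enrolment (Protocol 4.3), most children who entered the extension earlier would already have finished it.

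**The case against.** The strongest reply is that the plan already intends two runs: one on the core period, then an exploratory update with extension data. On the Extension Set every child is scheduled for the same 8 weeks after randomisation, so uptake would not distort follow-up there. This is a fair reading of Protocol 5.4.1 and SAP 15.3, but no text applies a Visit 3 cut to AEs, and the safety sections name a different set. The Extension Set is also self-selected after randomisation, so it cannot stand in for a comparison of all randomised children.

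Three further points stand and limit the severity. The safety objectives are descriptive (SAP 3.4) and no confirmatory testing is planned (SAP 8.1). The artefact may be smaller than chance variation. Unequal uptake would also be visible: disposition reports entry to and completion of the extension, reasons for declining are recorded, and event dates are listed with the randomisation date. That lets a reader notice the problem, but the AE table remains uncorrected.

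A reader might infer that uptake will differ by arm from this remark in Protocol 5.4.6: "The intervention period is limited to 4 weeks; a longer period may not be acceptable for families". It explains why the intervention lasts 4 weeks for everyone and says nothing about arms. A reader might also conclude that the safety comparison is biased as planned. The documents support only the conditional statement.

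**Conclusion.** The point holds as a conditional one. Both documents leave the between-arm AE proportions open to unequal follow-up, and nothing in the plan corrects for it. Distortion arises only if extension uptake differs between arms. Under equal hazards and a 10% risk per 4 weeks, the ratio on the Protocol window runs from 1.00 (equal uptake) through 1.12 (80% vs 60%) to 1.26 (80% vs 40%). On the SAP window the last case gives 1.15. Uptake and risk are assumptions, and no single value should be read as a forecast. Because the tables are descriptive, the consequence is for interpretation. This is a cheap improvement of low to moderate severity.

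**What to change.** In Protocol 5.4.4 and SAP 16.1:

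1. Make the between-arm display AEs with onset or worsening from randomisation to Visit 3 (or earlier discontinuation), with all randomised children per arm as denominator. Apply this cut in both the analysis at the end of the intervention period and the final one.
2. Show Visit 3 to Visit 4 separately and descriptively, with the Extension Set per arm as denominator.
3. Reconcile Protocol 5.4.1 (repeats on the Extension Set) with Protocol 5.4.4 and SAP 16 (Safety Analysis Set).
4. Reconcile the start of the TEAE window: randomisation in the Protocol, screening in the SAP. One row of SAP Appendix 1 still refers to randomisation while the others use screening.

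The cost is wording plus one extra table panel. AE start dates and visit dates are already collected. Differences in dropout before Visit 3 and the ±7-day visit window would remain, but the 4-week gap between decliners and entrants would not.
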